5. GENERAL METHODOLOGY AND CONVENTIONS

5.1. Hypotheses and Decision Rules

The null hypothesis to be tested concerns VE for the primary endpoints. RSVpreF will be compared to placebo, testing the hypotheses for each endpoint of H_{0i} : $VE \leq 20\%$ vs H_{ai} : $VE > 20\%$, where $i = 1$ denotes the MA-LRTI endpoint and $i = 2$ denotes the severe MA-LRTI endpoint. The overall primary null hypothesis is then $H_0 = H_{01} \cap H_{02}$. For all secondary efficacy endpoints, RSVpreF will be compared to placebo, testing the hypotheses $H_0: VE \leq 0\%$ vs $H_a: VE > 0\%$. Hypothesis testing of the secondary endpoints is conditional upon rejection of the null hypothesis for at least 1 of the primary endpoints.

The 2 primary endpoints of MA-LRTI due to RSV and severe MA-LRTI due to RSV will be tested in parallel using a Bonferroni multiplicity adjustment procedure, whereby half the available alpha is used on each of the 2 endpoints. Success of the trial requires rejection of the null hypothesis (ie, a CI lower bound $> 20\%$) for either of the 2 primary endpoints.

Testing of the 2 primary endpoints across the time intervals will follow a fixed sequence with a gatekeeping strategy. First, the hypothesis pertaining to the incidence of the 2 primary endpoints within 90 days after birth will be tested, at the full multiplicity-adjusted alpha level, using a Bonferroni adjustment. If the null hypothesis for both of the endpoints cannot be rejected, testing ends. Otherwise, testing proceeds with the incidence within 120 days after birth. Only primary endpoint(s) that are successful at all earlier time intervals will be considered at subsequent intervals. Testing will proceed to the endpoints evaluated at 150 days and 180 days, conditional on rejection of the null hypotheses for all earlier time intervals. In [Figure 1](#) a possible testing flow for the 2 primary endpoints at the final analysis is presented.

Figure 1. Example of Possible Testing Flow for Primary Endpoints at Final Analysis

α^* is the Type I error at final analysis adjusted for interim

Abbreviations: H_{01} = null hypothesis for the MA-LRTI endpoint; H_{02} = null hypothesis for the severe MA-LRTI endpoint; MA-LRTI = medically attended lower respiratory tract illness; VE = vaccine efficacy.

Inference for the secondary endpoints will be conditional upon demonstrating success through 180 days for 1 of the primary efficacy endpoints. The secondary endpoints of hospitalizations due to RSV, all-cause MA-LRTI, and MA-LRTI beyond 180 days will be tested in parallel so as to preserve the overall type I error across primary and secondary endpoint families at no more than 2.5% 1-sided. The alpha level available for the secondary endpoints will be dependent upon the results of the primary endpoints. If both primary endpoints are successful through 180 days, the full alpha will be available for the secondary endpoints. If only 1 of the 2 primary endpoints is successful through 180 days, half the alpha will be available. A Bonferroni multiplicity adjustment will also be used to analyze the 3 secondary endpoints in parallel. VE will be evaluated sequentially at 90 days, 120 days, 150 days, 180 days, and 360 days for hospitalization due to RSV and all-cause MA-LRTI and at 210 days, 240 days, 270 days, and 360 days for MA-LRTI due to RSV. In addition, the same fixed-sequence testing and gatekeeping strategy used for the primary endpoints will be employed.

5.2. General Methods

Descriptive summary statistics will be provided for all endpoints. Unless otherwise explicitly stated, descriptive statistics for continuous variables are n, mean, median, standard deviation, minimum, and maximum. Descriptive statistics for categorical variables are the percentage (%) and the n (the numerator) and N (the denominator) used in the calculation of the percentage.

All data will be summarized by vaccine group of the maternal participants. All data will be presented separately for maternal and infant participants. The only exception is the combined analysis of maternal-to-infant placental transfer ratio (infant/mother) of RSV A and RSV B serum neutralizing titers.

5.2.1. Analyses for Binary Endpoints

The number and percentage of participants in each category will be summarized. The 95% CI for percentage, and for the difference in percentages, will also be presented, where appropriate.

The analysis of efficacy will use a conditional exact test¹ based on the binomial distribution of the number of disease cases in the RSV vaccine group, given the total number of cases in both groups. The number of cases $x_i \sim P(\lambda_i)$, where $P()$ is the Poisson distribution ($i = 1$ denotes placebo, $i = 2$ denotes vaccine). It is known that $x_2|T = t \sim B(T, \pi)$, where $B()$ is the binomial distribution, $T = x_1 + x_2$ (the total number of events), and $\pi = \lambda_2 / (\lambda_1 + \lambda_2)$. Then, assuming equal numbers of participants per group, testing the hypothesis $H_0: VE \leq \theta$ is equivalent to testing $H_0: \pi \geq (1 - \theta) / (2 - \theta)$.

The 95% CI for proportions will be constructed by the Clopper-Pearson method described by Newcombe.² The 95% CI will be presented in terms of percentage.

The 95% CI for differences in the proportions will be computed using the Miettinen and Nurminen method.³ The 95% CI will be presented in terms of percentage.

5.2.2. Analyses for Continuous Endpoints

Unless otherwise specified, the CI for the mean of the continuous variables will be constructed by the standard method based on Student's t distribution.

5.2.2.1. Geometric Mean Titer

Continuous immunogenicity endpoints will be logarithmically transformed for analysis. The GMT and associated 2-sided 95% CI will be calculated at each available time point for each group. 95% CI for GMT will be obtained by exponentiating the limits of the 95% CI for the mean of the logarithmically transformed assay results computed using Student's t distribution.

5.2.2.2. Geometric Mean Fold Rise

The GMFR will be calculated by exponentiating the mean difference of an individual participant's logarithmically transformed titer levels (postvaccination minus prevaccination). 95% CI will be obtained by exponentiating the limits of the 95% CI for the mean difference of the logarithmically transformed assay results using Student's t distribution.

5.2.2.3. Geometric Mean Ratio

The GMR will be calculated by exponentiating the group mean difference of logarithmically transformed titer levels. 95% CI will be obtained by exponentiating the limits of the CIs for the mean difference of the logarithmically transformed assay results using Student's t distribution.

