3.3.2. Exploratory Endpoints – Maternal Participants

- The incidence of all-cause MA-RTIs from vaccination up to 180 days after delivery.
- RSV A and RSV B serum neutralizing titers and prefusion F IgG titers measured before vaccination and at the delivery visit.
- Ig concentrations against nonvaccine RSV antigens measured before vaccination and at delivery visit.

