3.4.2. Baseline Variables – Maternal Participants

Day 1 is defined as the day of vaccination for the maternal participants. Day 1 is considered the baseline visit for the maternal immunogenicity assessments.

Day 1 is the start of the reporting period for local reactions/systemic events. For prespecified systemic events, a baseline assessment related to the 1-week period prior to vaccination will also be recorded in the e-diary.

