6.3.1.10. RSV A and RSV B Serum Neutralizing Titers Measured at Birth

- Analysis set: Evaluable immunogenicity – infant (Section 4).
- Analysis methodology: Descriptive summary statistics. Results obtained from out-of-window blood draws will also be removed. Missing serology results will not be imputed, as MCAR is assumed. Only samples tested by the Pfizer central laboratory will be considered for this analysis.
- GMTs of the RSV A and RSV B serum neutralizing titers will be descriptively summarized for each vaccine group, along with associated 2-sided 95% CIs.
- GMTs of the combined RSV A/B serum neutralizing titer will be descriptively summarized for each vaccine group, along with associated 2-sided 95% CIs.
- GMRs of the RSV vaccine group to the placebo group for the RSV A and RSV B serum neutralizing titers will be calculated, along with associated 2-sided 95% CIs.
- GMR of the RSV vaccine group to the placebo group for the combined RSV A/B serum neutralizing titers will be calculated, along with associated 2-sided 95% CIs.
- Geometric means of the placental transfer ratio and associated 2-sided 95% CIs will be provided for RSV A, RSV B, and combined RSV A/B serum neutralizing titers. For each mother-infant dyad, the transfer ratio will be calculated as the ratio of the infant's RSV serum neutralizing titer at birth to the mother's RSV serum neutralizing titer at delivery. Group geometric means and CIs are calculated in the same way as for similar endpoints using the fold rise calculated above.
- A correlation scatterplot will be generated, with the infant blood titer on the x-axis and maternal titer on the y-axis.

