6.3.2.2.1. Main Analysis

- Analysis set: Evaluable immunogenicity maternal ([Section 4](#)).
- Analysis methodology: Descriptive summary statistics. Results obtained from out-of-window blood draws will also be removed. Missing serology results will not be imputed, as MCAR is assumed.
- GMTs of the RSV A and RSV B serum neutralizing titers at each available time point will be descriptively summarized for each vaccine group, along with associated 2-sided 95% CIs.
- GMT of the combined RSV A/B serum neutralizing titer at each available time point will be descriptively summarized for each vaccine group, along with associated 2-sided 95% CIs.
- GMFRs and associated 2-sided 95% CIs will be provided for RSV A and RSV B serum neutralizing titers from before vaccination to each available time point after vaccination for each vaccine group.
- GMFR and associated 2-sided 95% CIs will be provided for the combined RSV A/B serum neutralizing titers from before vaccination to each available time point after vaccination for each vaccine group.
- GMRs of the RSV vaccine group to the placebo group for the RSV A and RSV B serum neutralizing titers at each available time point after vaccination will be calculated, along with associated 2-sided 95% CIs.
- GMR of the RSV vaccine group to the placebo group for the combined RSV A/B serum neutralizing titer at each available time point after vaccination will be calculated, along with associated 2-sided 95% CIs.

- RCDCs for RSV A and RSV B serum neutralizing titers for a combination of prespecified time points and vaccine groups will be generated.

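### The vaccine/placebo GMRs for neutralizing titers make no use of the planned maternal prevaccination titer: the estimates are valid, but less precise than a baseline-adjusted model would give

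*SAP*

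**What the plan says.** Section 5.2.2.3 defines the point estimate: "The GMR will be calculated by exponentiating the group mean difference of logarithmically transformed titer levels". The interval comes from "exponentiating the limits of the CIs for the mean difference of the logarithmically transformed assay results using Student's t distribution". No covariate or model appears.

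Two analyses apply it. For mothers, Section 6.3.2.2.1 plans, for the postvaccination samples, "GMRs of the RSV vaccine group to the placebo group for the RSV A and RSV B serum neutralizing titers at each available time point", with a parallel item for the combined A/B titer. For infants, Section 6.3.1.10 states "GMRs of the RSV vaccine group to the placebo group for the RSV A and RSV B serum neutralizing titers will be calculated", again with a combined A/B item.

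The baseline measurement is part of the plan. Section 3.3.2 lists "RSV A and RSV B serum neutralizing titers and prefusion F IgG titers measured before vaccination and at the delivery visit", and Section 3.4.2 states "Day 1 is considered the baseline visit for the maternal immunogenicity assessments". In the summaries the prevaccination titer appears only by group, as a GMT time point, in the distribution curves, or through the fold rise: "GMFRs and associated 2-sided 95% CIs will be provided for RSV A and RSV B serum neutralizing titers from before vaccination to each available time". The SAP contains no baseline-adjusted immunogenicity model. The sensitivity analysis that follows the maternal main analysis removes data after RSV infection; it does not adjust for baseline.

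The point is confined to neutralizing titers, because Sections 6.3.1.12 and 6.3.2.3 plan no between-group ratio for prefusion F IgG.

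**The concern.** The prevaccination titer is measured before treatment and is a plausible source of spread between mothers in the titers measured later. If it correlates at all with the delivery or birth titer, a comparison that conditions on it has smaller variance than a raw difference of means, at no cost in extra samples. The SAP plans the measurement but uses it only within each group. The fold rise does not fill the gap: it is a within-group quantity with no between-group interval. Under Section 5.3.2, when only one of the two values is below LLOQ, it is set to half LLOQ in the numerator but to LLOQ in the denominator, so dividing one arm's GMFR by the other's is not a clean adjusted contrast.

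What is at stake is the width of the GMR intervals, and how far a chance difference in baseline between arms moves the point estimate when few participants contribute. Section 6.4 allows testing on subsets first, possibly reported separately. Table 10 lists immunogenicity endpoints for infants by country, income level and gestational age at vaccination, and for mothers and infants by age below 18 years. The SAP gives no size for any of these cells.

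**Working it through.** The SAP states no SD, correlation, sample size or precision target for the GMR, so there is no planned figure to reproduce. The check asks how much precision adjustment would add.

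**Inputs from the SAP.** Allocation 1:1 and about 6900 mother-infant pairs, hence 6900 / 2 = 3450 per arm if all are tested (Section 2.2).

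**Assumed inputs.** SD of log10 titer 0.4 (range 0.3 to 0.5); within-arm correlation ρ between log baseline and log outcome 0.3 to 0.7; 150 and 500 per arm as illustrative smaller sets.

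**Relative gain.** With 1:1 allocation and a common ρ, adjustment multiplies the variance of the log difference by 1 − ρ². The interval narrows on the log scale by 1 − √(1 − ρ²), and the equivalent increase in sample size is 1/(1 − ρ²) − 1.

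| ρ | Variance ratio | Log-scale interval narrower by | Equivalent extra participants |
|---|---|---|---|
| 0.3 | 0.91 | 5% | 10% |
| 0.5 | 0.75 | 13% | 33% |
| 0.7 | 0.51 | 29% | 96% |

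In 4000 simulated trials with 150 per arm the variance ratios were 0.91, 0.77 and 0.51, and both estimators were unbiased. If the arms have different correlations but equal SDs, the ratio is 1 − ((ρ_vaccine + ρ_placebo)/2)². For example, 0.4 and 0.8 give 1 − 0.6² = 0.64.

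**Absolute gain.** The 95% interval multiplies and divides the GMR by 10^(t × SD × √(2/n) × √(1 − ρ²)). At n = 150, SD 0.4 and ρ = 0, SD × √(2/n) = 0.4 × 0.1155 = 0.0462. With t = 1.968 the exponent is 0.0909 and the factor is 1.233. With ρ = 0.5 the exponent is 0.0909 × 0.866 = 0.0787 and the factor is 1.199.

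| n per arm (SD 0.4) | Unadjusted | Adjusted, ρ = 0.5 | Adjusted, ρ = 0.7 |
|---|---|---|---|
| 3450 | 1.044 | 1.038 | 1.032 |
| 500 | 1.121 | 1.104 | 1.085 |
| 150 | 1.233 | 1.199 | 1.161 |

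With SD from 0.3 to 0.5, the unadjusted factor runs from 1.033 to 1.056 at 3450 per arm and from 1.17 to 1.30 at 150 per arm.

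**Chance baseline difference.** The 95% range of the shift it causes in the unadjusted GMR is a factor of 10^(1.96 × ρ × SD × √(2/n)). At SD 0.4 and ρ = 0.5 this is 1.022 at 3450 per arm, 1.059 at 500 and 1.110 at 150. At ρ = 0.7 it is 1.031, 1.083 and 1.157. The unadjusted interval already allows for this variation; adjustment largely removes it.

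**The case against.** The strongest reply is that this is a choice and not an error. The unadjusted difference of log means is unbiased under randomization, and its interval has correct coverage. The endpoints are exploratory and summarized descriptively, and no hypothesis, alpha or precision target depends on the GMR. With everyone tested, the intervals are already very tight and the factor changes by about 1% or less. Maternal baseline GMTs are shown by group, so an overall imbalance would be visible. All of this stands, and it fixes the severity as low. It does not remove the gain, which follows for any nonzero correlation.

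Several stronger readings are tempting but unsupported:

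- A reader might infer that chance baseline imbalance biases the GMR or invalidates its interval. It does neither.
- A reader might take baseline titer to be the main source of between-mother spread. The SAP says nothing on this and gives no correlation, for cord titers in particular.
- A reader might assume that all subgroup intervals for mothers suffer. Table 10 lists only infant immunogenicity for country and gestational age, and it names immunogenicity endpoints in general without specifying subgroup GMRs.
- A reader might assume that a valid baseline exists for everyone analysed. The Section 4 definitions do not explicitly require a prevaccination result for the evaluable maternal set, and the infant set requires no maternal titer. An adjusted model therefore needs a rule for missing baselines.

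**Conclusion.** The point holds as a low-severity efficiency improvement. The SAP specifies an unadjusted between-group GMR while planning a maternal baseline titer that could sharpen it. The relative gain on the log scale is about 5%, 13% or 29% at correlations of 0.3, 0.5 or 0.7. In absolute terms it is negligible if about 3450 per arm are tested (1.044 to 1.038 at correlation 0.5) and modest at an illustrative 150 per arm (1.233 to 1.199). These figures rest on an assumed SD of 0.4 log10, assumed correlations and an assumed subset size, none of which the SAP gives. The planned GMR is not wrong, and nothing in the efficacy conclusions depends on it.

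**What to change.** In Section 5.2.2.3, estimate the GMR from a linear model of log titer on vaccine group with the mother's log prevaccination titer as covariate, and refer to it from Sections 6.3.2.2.1 and 6.3.1.10. Three details should be fixed before unblinding:

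- **Unequal slopes:** use robust standard errors, or include a group-by-centred-baseline term.
- **Missing baselines:** state a rule that keeps everyone in the model, for example a missing indicator or a single-value imputation made without reference to arm.
- **Values below LLOQ:** enter them as half LLOQ, as Section 5.3.2 does for GMTs.

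Keep the present unadjusted GMR as a supplementary row. The cost is a few sentences of SAP text and slightly more programming, with no new data collection. The downside is that the gain may be small, especially for cord titers.

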5.2.2.4. Reverse Cumulative Distribution Curves

RCDCs for RSV A and RSV B serum neutralizing titers for a combination of available time points and vaccine groups will be generated.

5.3. Methods to Manage Missing Data

Standard algorithms on handling missing AE dates and missing AE severity will be applied as described in Pfizer's Vaccine Statistics Rulebook.

5.3.1. Reactogenicity Data

For derived variables based on reactogenicity data, if any day of the 7-day e-diary is available, the "any day (Day 1-7)" data will be considered nonmissing.

The reactogenicity data are collected through the e-diary, which does not allow participants to skip the question. Therefore, for a specific day, as long as the e-diary data are transferred for that day, all of the reactogenicity data for the participant on that day are nonmissing. No missing reactogenicity data will be imputed other than what is described in [Section 3.5.2](#).

5.3.2. Immunogenicity Data

For GMT and GMC analysis, a titer reported as < LLOQ will be converted to a value of $\frac{1}{2}$ LLOQ (LLOQ values for each assay are presented in [Table 7](#)). Serology data transfers will include LLOQ values applicable to all assays reported, and may supersede the values shown here. For calculating a fold rise, < LLOQ will be converted to $\frac{1}{2}$ LLOQ for a numerator, and < LLOQ will be converted to LLOQ for a denominator when only 1 of either the numerator or denominator is < LLOQ.

If both the numerator and denominator are < LLOQ, then both will be converted in the same way. For any calculations, a titer reported as > ULOQ will be converted to a value of ULOQ.

Values that are designated as serum QNS, designated as indeterminate results, or recorded as "not done" will be set to missing. No imputation will be done for these missing values.

Table 7. LLOQ Values

Assay	LLOQ Value
RSV A 50% serum neutralizing titer	50
RSV B 50% serum neutralizing titer	70
RSV A 90% serum neutralizing titer	50
RSV B 90% serum neutralizing titer	55
Anti-RSV A prefusion F IgG	2.620
Anti-RSV B prefusion F IgG	2.620
Anti-Ga RSV nonvaccine-antigen Ig	0.490
Anti-Gb RSV nonvaccine-antigen Ig	0.490
Anti-M RSV nonvaccine-antigen Ig	0.490
Anti-N RSV nonvaccine-antigen Ig	0.550

Abbreviations: Ig = immunoglobulin; IgG = immunoglobulin G; LLOQ = lower limit of quantitation; RSV A = respiratory syncytial virus subgroup A; RSV B = respiratory syncytial virus subgroup B.

5.3.3. Efficacy Data

Cases that qualify as MA-LRTI events based on clinical signs and symptoms but do not have a valid RSV swab result will be identified. Sensitivity analyses of the primary endpoints will be done under various assumptions about the missing swab results. In each scenario, cases with imputed positive RSV results will be added to the confirmed RSV-positive cases and vaccine efficacy in the augmented set of cases analyzed.

Based on a blinded review of swab results at the end of February 2022, approximately 22% of all swabs from MA-LRTI events with valid central lab results cases proved to be RSV-positive. Thus, a minority of the missing results are expected to be truly RSV-positive, and imputation scenarios will include:

- Missing swab results are assumed to be positive in the same proportion (by vaccine group) as the nonmissing swab results in MA-LRTI events (missing-at-random assumption).
- For the vaccine group, missing swab results are assumed to be positive in higher proportions than the nonmissing swab results in MA-LRTI events, while in the placebo group missing swab results are assumed to be positive in the same proportion as the nonmissing swab results in MA-LRTI events (missing-not-at-random assumption). A range of higher vaccine group positivity rates will be assumed.

Multiple imputations will be performed to randomly assign missing swab results. SAS PROC MI will be used to generate 500 imputed data sets for each scenario. Mean and median VE across imputations, and the proportion of imputations with VE lower bound >20% will be reported.

5.4. Endpoint Events and Definitions

5.4.1. Endpoint Events and Definitions – Infant Participants

The study endpoints for infant participants employ the event definitions in Table 8.

Table 8. Primary and Secondary Endpoint Events and Definitions in Infant Participants

Study Endpoint/Assessment	Study Definition
Medically attended visit	Infant participant has been taken to or seen by a healthcare provider (eg, outpatient or inpatient visit, emergency room, urgent care, or home visit).
MA-RTI visit for infant participant	A medically attended visit AND 1 or more of the following RTI signs and symptoms: 
 • Nasal discharge for 24 hours or more • Difficulty breathing, labored breathing, or rapid breathing for any duration • Cough • Inability to feed for any duration because of respiratory symptoms • Apnea • Any other respiratory symptom of concern
RSV-positive test ^a	
 • RSV RT-PCR–positive test result by Pfizer central laboratory OR • RSV-positive test result by certified^b laboratory with NAAT for RSV
MA-RTI due to RSV ^a	
 • An MA-RTI visit AND • RSV-positive test result as described in Section 8.1.1.1 of the protocol
MA-LRTI due to any cause	
 • Infant with an MA-RTI visit AND • Fast breathing (respiratory rate \geq60 bpm for <2 months of age [<60 days of age], \geq50 bpm for \geq2 months to < 12 months of age, or \geq40 bpm for \geq12 months to 24 months of age) OR • SpO₂ <95% OR • Chest wall indrawing

Table 8. Primary and Secondary Endpoint Events and Definitions in Infant Participants

Study Endpoint/Assessment	Study Definition
MA-LRTI due to RSV ^a	
 • Infant with an MA-RTI visit AND • Fast breathing (respiratory rate ≥ 60 bpm for <2 months of age [<60 days of age], ≥ 50 bpm for ≥ 2 months to < 12 months of age, or ≥ 40 bpm for ≥ 12 months to 24 months of age) OR • SpO₂ <95% OR • Chest wall indrawing AND • RSV-positive test result as described in Section 8.1.1.1 of the protocol
Hospitalized RTI due to RSV ^a	
 • An RTI due to RSV that results in hospitalization
Severe MA-LRTI due to RSV ^a	
 • Infant with an MA-RTI visit AND • Fast breathing (respiratory rate ≥ 70 bpm for <2 months of age [<60 days of age], ≥ 60 bpm for ≥ 2 months to < 12 months of age, or ≥ 50 bpm for ≥ 12 months to 24 months of age) OR • SpO₂ <93% OR • High-flow nasal cannula or mechanical ventilation (invasive or noninvasive) OR • ICU admission for >4 hours OR • Failure to respond/unconscious AND • RSV-positive test result as described in Section 8.1.1.1 of the protocol
Protocol-defined primary endpoint	
 • Any MA-LRTI or severe MA-LRTI due to RSV as determined by EAC^c

Abbreviations: EAC = endpoint adjudication committee; ICU = intensive care unit; MA-LRTI = medically attended lower respiratory tract illness; MA-RTI = medically attended respiratory tract illness; NAAT = nucleic acid amplification test; RSV = respiratory syncytial virus; RTI = respiratory tract illness; RT-PCR = reverse transcription–polymerase chain reaction; SpO₂ = oxygen saturation as measured by pulse oximetry.

- a. The EAC will determine if the endpoint criteria have been met upon review of the site source documentation from the MA-RTI and RTI study visits, including all available RSV test results.
- b. See the EAC charter for more details regarding the certified laboratory.
- c. Severe MA-LRTI cases that are adjudicated by the EAC will always be MA-LRTI cases (severe MA-LRTIs are a subset of the MA-LRTIs).

